3.3. GATEKEEPING PROCEDURE

A parallel gatekeeping testing procedure will be used to protect the overall type I error rate of α (alpha) when testing the primary endpoint together with the key secondary endpoints between each glepaglutide treatment group versus placebo. The twice weekly treatment group and once weekly treatment group comparisons to placebo will be tested by splitting α into 2 $\alpha/2$ comparisons at the appropriate step within the testing procedure.

The confirmatory testing strategy follows the approach by Bretz et al 2011. Loosely described, the gatekeeping procedure starts by identifying the smallest maximum p-value of the first three tests (primary efficacy endpoint, 1st key secondary endpoint, and 2nd key secondary endpoint), among the two dosing regimens, once- and twice-weekly. For this regimen, the primary efficacy endpoint, 1st key secondary endpoint, and 2nd key secondary endpoint are evaluated at an $\alpha/2$ significance level sequentially, only continuing to the next evaluation if the preceding test is statistically significant. If all of the first three tests result in p-values less than or equal to $\alpha/2$, the procedure continues at an α level for the other regimen. If all of the three tests for the other regimen, and the procedure continues at an $\alpha/2$ level for the other regimen. If all of the three tests for the other regimen result in p-values less than or equal to $\alpha/2$, the procedure continues at an $\alpha/2$ level for the other regimen. If all of the three tests for the other regimen, and the procedure continues less than or equal to $\alpha/2$, the procedure continues at an $\alpha/2$ level for the other regimen. If all of the three tests for the other regimen result in p-values less than or equal to $\alpha/2$, the procedure continues at an $\alpha/2$ level for the other regimen. If all of the three tests for the other regimen result in p-values less than or equal to $\alpha/2$, the procedure continues where it was previously stopped, at α level for the first regimen.

Depending upon the results for the first three endpoints in the regimen where the procedure begins, the significance level is specified for the other regimen at $\alpha/2$ or at α . The sequential testing procedure then continues for the first three endpoints in the other regimen. If all six hypotheses (three first endpoints from both regimens) are significant, the last two key secondary endpoints are evaluated sequentially at the α significance level, only continuing to the next evaluation if the preceding is statistically significant. The parallel gatekeeping procedure is displayed below in Figure 1.

Figure 1 Testing hierarchy

3.4. SECONDARY EFFICACY ENDPOINTS

The following secondary efficacy endpoints will additionally be analyzed to assess the treatment effect using the FAS. Actual PS volume will be used in the analyses. The tests will be non-hierarchical and type I error will not be adjusted for multiple testing:

Change of at least 20% in actual weekly PS volume from baseline to both Weeks 12 and 24

The difference in response in reduction of $\geq 20\%$ in PS volume from baseline to both Weeks 12 and 24 between each glepaglutide treatment group versus placebo will be analyzed in a similar manner as the first key secondary efficacy endpoint.

Change in calculated energy content of parenteral macronutrients from baseline to Week 24

The calculated energy content provided by PS in kcal and in kcal/kg of body weight will be summarized descriptively at baseline and at Week 24 and include the number of non-missing observations, mean, SD, median, minimum, and maximum values.

For a given visit the calculated energy content will be derived as the sum of lipids, glucose and

25 August 2022

amino acids recorded in the eDiary during the valid 7-day period used for deriving the actual weekly PS volume. The change in calculated energy content of parenteral macronutrients from baseline to Week 24 will be analyzed with an MMRM model similar to the one specified for the primary efficacy endpoint. The analysis will be conducted for the calculated energy content in kcal and kcal/kg, separately.

As supporting analyses the calculated energy content (in each unit separately), will be derived based on the records in the eDiary during the valid 14-day period used for the deriving the actual weekly PS volume endpoint on a 14-day period.

Change in number of days on actual PS per week from baseline to Week 24

The difference in change in the number of days on PS per week from baseline to Week 24 between each glepaglutide treatment group relative to placebo will be analyzed with an MMRM model similar to the one described for the primary endpoint.

Reduction of at least 40% in actual weekly PS volume from baseline to both Weeks 20 and 24

The difference in response in reduction of $\geq 40\%$ in PS volume from baseline to both Weeks 20 and 24 between each glepaglutide treatment group comparison to placebo will be tested using the CMH test adjusted for the stratification factor will be analyzed in a similar manner as the clinical response endpoint (first key secondary endpoint).

Reduction of at least 30% in actual weekly PS volume from baseline to both Weeks 20 and 24

The difference in response in reduction of $\geq 30\%$ in PS volume from baseline to both Weeks 20 and 24 between each glepaglutide treatment group comparison to placebo will be tested using the CMH test adjusted for the stratification factor will be analyzed in a similar manner as the clinical response endpoint (first key secondary endpoint).

Reduction in prescribed weekly PS volume of 100% (weaned off) at Week 24

The difference in response in prescribed weekly PS volume of 100% (weaned off) at Week 24 between each glepaglutide treatment group comparison to placebo will be tested using the CMH test adjusted for the stratification factor will be analyzed in a similar manner as the weaned off endpoint based on actual PS volume (fourth key secondary endpoint).

PGIC improvement at weeks 4, 12, 20, and 24

PGIC improvement is defined as responding "Very Much Improved" or "Much Improved" on a 7-point Likert Scale for each of the weeks 4, 12, 20, and 24. Improvement between each glepaglutide treatment regimen compared to placebo will be tested by week, using the CMH test adjusted for the stratification factor. In similar fashion, improvement between each glepaglutide treatment regimen versus placebo will be tested using collapsed categories of Improvement, No Change, and Worsening, where Improvement is defined as a response of "Very Much Improved" or "Much Improved" or "Minimally Improved", and No Change is defined as the response of "No Change", and Worsening is defined as a response of "Minimally Worse" or "Much Worse" or "Very Much Worse". Improvement using collapsed 25 August 2022 Confidential Page 24 of 65

categories between each glepaglutide treatment regimen compared to placebo will tested by week using a Mantel-Haenszel chi-squared test for ordered categories. No imputation for missing values will be performed.

Change in weight from baseline to Week 24

The change in body weight (kg) from baseline to Week 24 will be presented descriptively by baseline BMI subgroup. Descriptive statistics will include the number of non-missing observations, mean, SD, median, minimum, and maximum values. A shift table by BMI subgroup from baseline to Week 24 will be presented. The BMI subgroups are defined as: <18.5 kg/m2, \geq 18.5 to <25 kg/m2, \geq 25 to <30 kg/m2 and \geq 30 kg/m2.

The change in body weight (kg) from baseline to Week 24 will also be presented by three groups: less than 5% change, 5% to 10% change, and greater than 10% change.

Prescribed weekly PS volume

The prescribed weekly PS volume at baseline, Weeks 1, 2, 4, 8, 12, 16, 20, and 24 will be defined as the prescribed weekly PS volume received during the 7-day period prior to these visits.

The source for the derivation will be the prescribed PS volume information recorded in the eCRF by the investigator; for details on the derivation see Appendix A.

The change in prescribed weekly PS volume from baseline to Week 24 will be analyzed with the same statistical methodology as for the primary analysis of the primary endpoint.

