If endpoint not set to missing and no. of PS entry days \neq 7, missing PS entry days will be imputed with	0	Average of non-missing days	0	0	Tipping (from 0 to 1 by 0.1)*Average of non- missing days
Flexible window for endpoint assessment	7 consecutive days within the period between 1 and 14 days preceding visit date (30 days for baseline)	7 consecutive days preceding visit date	7 consecutive days within the period between 1 and 14 days preceding visit date (30 days for baseline)	7 consecutive days within the period between 1 and 14 days preceding visit date (30 days for baseline)	7 consecutive days preceding visit date
Allow window for endpoint assessment to cross previous visit	No (with exemption of Week 1 and 2)	Yes	No (with exemption of Week 1 and 2)	No (with exemption of Week 1 and 2)	Yes
Information from NTFs used	Yes	No	No	Yes	No

Abbreviations: PS: parenteral support, NTF = note-to-file

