3.5. OTHER EFFICACY ENDPOINTS

The following other efficacy endpoints will be summarized to assess the treatment effect using the FAS.

The endpoints related to the number of days on actual PS a week will be derived using the selected valid 7-day period used for the primary endpoint. Additionally to summary statistics, these endpoints will be analyzed with the same methodology as for the primary analysis of the confirmatory binary endpoints.

Reduction in days on actual $PS \ge 2$ days per week from baseline to Week 24

The number and percent of patients who have a reduction in days on $PS \ge 2$ days per week from baseline to Week 24 will be presented for each glepaglutide treatment group and placebo

Reduction in days on actual PS \geq 3 days per week from baseline to Week 24

The number and percent of patients who have a decrease in days on $PS \ge 3$ days per weekfrom baseline to Week 24 will be presented for each glepaglutide treatment group and25 August 2022ConfidentialPage 25 of 65

placebo.

Change in duration of actual PS infusions per week from baseline

The change will be presented as descriptive statistics at Weeks 1, 2, 4, 8, 12, 16, 20, and 24.

Concentration trough levels of glepaglutide and metabolites

Concentration trough levels of glepaglutide and metabolites will be summarized descriptively. The number of non-missing observations, mean, SD, median, minimum, and maximum values will be presented by visit.

Change in plasma citrulline levels from baseline to Week 24

The change in plasma citrulline levels from baseline to Week 24 will be presented descriptively and include the number of non-missing observations, mean, SD, median, minimum, and maximum values.

Change in weekly need for parenteral micronutrients (sodium, potassium, magnesium, and calcium) from baseline to Week 24

The change in weekly need for parenteral micronutrients from baseline to Week 24 will be summarized using number of non-missing observations, mean, SD, median, minimum, and maximum values for sodium, potassium, magnesium, and calcium.

For a given visit the parental micronutrients content will be derived from the eDiary values recorded during in valid 7-day period used for deriving the actual weekly PS volume.

Actual PS intake of micronutrients will be used for the analysis involving PS content. Each of the 4 micronutrients will be summarized separately (for sodium, potassium, magnesium, and calcium).

Change in PROs (SBS-I and EQ-5D-5L) from baseline to Week 24

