The weekly PS volume accounted for is derived as the actual volume in a valid 7-day period prior to the relevant visit plus prescribed volumes documented not taken (via notes to file) during the same period. Hereafter referred to as the *volume accounted for*.

The relevant prescribed volume is derived as the sum of the prescribed volumes during the valid 7-day period divided by 7 (to account for the volumes being recorded in L/week). Hereafter referred to as the *relevant prescribed volume*.

The steps to select a valid 7-day period and derive AVAL related to an attended visit are as follows:

- 1. The first period considered will be the 7-days period from the visit date minus 1 day to the visit date minus 7 days.
- 2. A valid period cannot start before the previous visit for post-baseline visits (before the last optimization visit for baseline visits). If the considered period starts before the previous visit date then, AVAL will be set to missing, ANLxxFL is set to ' ' and ANLxxREA = "Period starts before previous visit" and the loop stops.

Note that, the exemption to this rule will be that a Week 1 valid period will be allowed to start prior to the date of visit Day 3 (which is not included in the dataset) or baseline visit, and Week 2 valid period will be allowed to start prior to the dates of visits Week 1 or Day 3 (which is not included in the dataset).

- 3. Else, if there is at least one volume accounted for at each day in the eDiary for the period, then the period is considered valid, AVAL is derived as specified above, and ANLxxFL is set to 'Y' and the loop stops.
- 4. Else, if for the period, the volume accounted for is ≥ 90% of the relevant prescribed volume, then the period is considered valid, AVAL is derived as specified above, and ANLxxFL is set to 'Y' and the loop stops.

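### The energy endpoint uses diary windows that are never checked for nutrient content, so in mixed regimens an unrecorded nutrition bag can be scored as lower energy intake

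*SAP*

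**What the plan says.** SAP 3.4 lists the change in calculated energy content as a secondary endpoint and tests it with an MMRM, outside the gatekeeping and without multiplicity adjustment. Energy is the sum of lipids, glucose and "amino acids recorded in the eDiary during the valid 7-day period used for deriving the actual weekly PS volume". SAP 3.5 uses the same window for sodium, potassium, magnesium and calcium, with values "derived from the eDiary values recorded during in valid 7-day period used for deriving the actual weekly PS volume"; these are only summarised descriptively.

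SAP Appendix A chooses the window on volume, by either of two routes:

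- Step 3: "if there is at least one volume accounted for at each day in the eDiary for the period, then the period is considered valid".
- Step 4: "if for the period, the volume accounted for is ≥ 90% of the relevant prescribed volume, then the period is considered valid".

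The volume accounted for is the recorded volume "plus prescribed volumes documented not taken (via notes to file) during the same period". Table 5 in SAP 3.1.4 shows that, in the main derivation, "missing PS entry days will be imputed with" zero. A bag that was never entered therefore adds nothing to the volume sum, and nothing to a nutrient sum over the same records.

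The only robustness step for energy is a repeat on the 14-day window, which is chosen by the same volume rule.

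**The concern.** Volume is a weak guide to energy when a patient receives both fluid and nutrition bags. The documents allow for such regimens. SAP Appendix A lets a prescription hold several bag identifiers, and the classification in Protocol 19.1 treats energy and volume as separate axes, including a class with no energy and more than 3 L/day. A window can be nearly complete for volume and far from complete for energy.

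What is at stake is how a volume reduction is read. The energy endpoint helps show whether support was cut in fluid only or in nutrition as well. A diary gap at a post-baseline visit appears as a cut in calories; a gap at baseline lowers the starting value and masks a real cut.

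Volume has four supportive derivations (SAP 3.1.4) and a counterpart based on prescription (SAP 3.4). Energy has neither, although Protocol 11.2.3 names the prescribed regimen as a source for calories and nutrients.

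**Working it through.** The plan states no figure on this point, so there is none to reproduce. The check applies the Appendix A rule directly.

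**Inputs from the documents.** The 90% volume threshold and the daily-entry route (SAP Appendix A); unrecorded intake counted as zero (SAP 3.1.4, Table 5); a typical need of 10 to 18 L/week (Protocol 4.1).

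**Assumed inputs.** Bag volume b from 0.5 to 2.0 L, and k nutrition bags per week of equal energy, k from 2 to 7. The documents give neither.

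**Step 4, one bag missed.** With prescribed volume W, the window passes if (W − b)/W ≥ 0.90, that is, if b ≤ 0.10 × W. Percentage of volume recorded:

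| W (L/week) | b = 0.5 L | b = 1.0 L | b = 1.5 L | b = 2.0 L |
|---|---|---|---|---|
| 6 | 91.7 pass | 83.3 fail | 75.0 fail | 66.7 fail |
| 8 | 93.8 pass | 87.5 fail | 81.3 fail | 75.0 fail |
| 10 | 95.0 pass | 90.0 pass | 85.0 fail | 80.0 fail |
| 12 | 95.8 pass | 91.7 pass | 87.5 fail | 83.3 fail |
| 15 | 96.7 pass | 93.3 pass | 90.0 pass | 86.7 fail |
| 18 | 97.2 pass | 94.4 pass | 91.7 pass | 88.9 fail |

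**Energy lost when the missed bag is a nutrition bag.** The shortfall is 1/k: 50% for k = 2, 33.3% for k = 3, 20% for k = 5, 14.3% for k = 7. Example: 12 L/week made of nine 1 L fluid bags and three 1 L nutrition bags, with one nutrition bag unlogged. Volume is 11/12 = 91.7%, so the window is valid; energy is 2/3 = 66.7% of the true value, understated by 33.3%.

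**Step 3.** There is no percentage test. In the same example, let the nine fluid bags cover all seven days and all three nutrition bags go unlogged. Recorded volume is 9/12 = 75%, yet the window is valid because each day has an entry, and energy reads zero.

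**Where the problem does not arise under step 4.** If all m bags are equal and all carry nutrition, one missed bag is 1/m of volume: 33.3% for m = 3 and 14.3% for m = 7, both rejected. It passes only from m = 10, when the energy loss is at most 10%.

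**14-day version.** One missed bag costs 1/(2k) of energy: 25% for k = 2, 16.7% for k = 3. The tolerated bag rises to 0.10 × 2W = 0.20 × W, which is 2.0 L at 10 L/week.

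**Under a 90% energy check on the 7-day window.** One missed bag leaves (k − 1)/k accounted for: 50% (k = 2), 66.7% (k = 3), 80% (k = 5), 85.7% (k = 7). All fall below 90%, so each would be caught.

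**The case against.** The strongest reply is that the result is conditional and its frequency unknown. Under step 4 the missed bag must be no more than 10% of weekly volume, and energy must sit in few bags. The table shows many combinations that fail the test. This stands: a reader might infer that any unrecorded nutrition bag gets through, and the documents do not support that.

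Conduct safeguards also exist. Protocol 7.4 requires actual use to match prescription in content as well as volume before randomization. Protocol 10.4 has the investigator review the diary before visits and reschedule if data are absent, and Protocol 11.2.1 requires discrepancies to be clarified with the patient. These make whole-bag gaps less likely, but they do not replace a derivation rule.

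The 14-day analysis is not useless: for a single missed bag it halves the error, so a gap between the 7-day and 14-day results could give a hint. It still tests no content, and it admits a larger bag.

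A reader might also infer bias in favour of glepaglutide. The arms are blinded and share one rule, and a baseline gap works in the opposite direction, so what is shown is mainly noise. Balance is not guaranteed, because the tolerance scales with a prescribed volume that treatment is meant to change. Assuming a 12 L/week baseline and the mean changes in Protocol 12.7, it would be 0.10 × (12 − 4.5) = 0.75 L on twice-weekly glepaglutide and 0.10 × (12 − 2.3) = 0.97 L on placebo. Nothing in the documents fixes the direction of any resulting difference.

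**Conclusion.** The gap is real and limited. The SAP accepts windows for the energy endpoint with no check on nutrient content, and in mixed regimens an unrecorded nutrition bag can pass and be scored as lower intake. For a 1 L bag at 10 to 18 L/week the understatement is 50%, 33% or 20% with 2, 3 or 5 nutrition bags per week. Step 3 sets no limit. These sizes rest on assumed bag volumes and equal energy per bag. How often such gaps occur cannot be judged from the documents.

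Two stronger readings are not supported. The first is a large false cut in electrolytes: electrolytes may come from the fluid bags too, no bag composition is given, and the micronutrient summaries are descriptive. The second is a threat to the trial's main conclusions: energy lies outside the gatekeeping, and the primary and key secondary endpoints do not use nutrient content.

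**What to change.** In SAP 3.4, keep the window that Appendix A selects on volume, so that volume and energy describe the same week. Add a content check for energy only, at baseline and at each later visit. Divide the energy recorded or documented as not taken by the energy prescribed in that window, and set energy to missing if the ratio is below 90%. State that the check does not apply where prescribed energy is zero. At minimum, pre-specify this as a sensitivity analysis alongside an analysis of prescribed energy content. The micronutrient summaries need no windows of their own, and the volume endpoint stays as it is.

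No new data should be needed: the diary holds the bag name (Protocol 8.4) and the eCRF holds the type and content of the prescribed support (Protocol 8.7). The work is a few lines of SAP text, derivation code, and linking notes to file to the energy of the bags concerned. A rule for missing baseline energy is also needed, since the one in SAP 3.1 is written for PS volume. The downside is a few more missing energy values, some of them from genuine under-use that nobody documented.
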